All participants will be compensated for their time and inconvenience of study participation according to the schedule below:

- Screening 1a: \$25
- Screening 1b: \$20
- Follow-Up Visits: $\$50 \times 8 = \400
- Rectal/Vaginal Biopsy Visit: \$125
- Optional Rectal Biopsy (Women Only): \$50
- Unscheduled Visit (if needed): \$20
- Total: \$570

If participants do not finish the study, they will be compensated for the visits they have completed.

Because Visits 2-5 take place over a span of 8 hours, we will provide participants with a \$15 gift card while they wait, for food and/or incidentals.

Compensation will be provided on a web-based, reloadable, debit card (ClinCard) that automates reimbursements. The ClinCard will be provided by study staff at the participants' initial visit (visit 1), and funds will be loaded after the completion of each visit.

There is no charge for parking at the Hope Clinic. However, participants may be provided with a MARTA card or other transportation resource (e.g. rideshare), if available.

18. Data Management and Confidentiality

Confidentiality

Case report forms (CRFs) will be used to collect demographic, behavioral, clinical, and laboratory data at study visits. Upon enrollment, each participant will be assigned a unique Participant Identification (PID) number. All laboratory specimens, CRFs, reports, and other records that leave the site will be identified only with the assigned PID. All study samples and records (both identifiable and not identifiable) will be kept in a secure area in a limited-access facility that only authorized study personnel have access to. Electronic data will be password protected and stored in REDCap or other Emory-sponsored HIPAA-compliant system. Information about the subject's participation will not be shared with individuals who are not directly involved with participants. Clinical information will not be released without written permission of the subject, except as necessary for monitoring by the IRB, the FDA, the NIH, the CDC or OHRP.

Quality Assurance Data Monitoring

Hope Clinic QA staff will monitor data periodically for data quality and protocol compliance. Twice yearly, study staff will conduct a systematic review of study data using the Emory University-Self-monitoring Tool available at http://www.ctac.emory.edu/clinical_trial_resources/Audit%20Tools.html.

Statistical Analysis Plan

Primary Outcomes: Comparison of doxycycline concentrations in blood and tissue between men and women. Plasma doxycycline concentrations at 24 hours will be compared between men and women using a Wilcoxon test. Median rectal and vaginal swab doxycycline concentrations collected at 24 hours after dosing will be compared using a Wilcoxon test. Median rectal and cervical tissues doxycycline concentrations collected at 24 hours after dosing will be compared using a Wilcoxon test. P-values less than 0.05 will be considered significant.

Exploratory Outcomes: Comparison of TAF, FTC, and BIC concentrations in blood and tissue between men and women. Plasma TAF, FTC, and BIC concentrations at 24 hours will be compared between men and women using a Wilcoxon test. Median rectal and vaginal swab TAF, FTC, and BIC concentrations collected at 24 hours after dosing will be compared using a Wilcoxon test. Median rectal and cervical tissue TAF, FTC, and BIC concentrations collected at 24 hours after dosing will be compared using a Wilcoxon test. P-values less than 0.05 will be considered significant.

19. Provisions to Monitor the Data to Ensure the Safety of Participants

Adverse Events

An Adverse Event (AE) as any untoward medical occurrence in a clinical investigation subject administered a pharmaceutical product regardless of its causal relationship to the study treatment. An AE can therefore be any unfavorable and unintended sign (including an abnormal laboratory finding), symptom or disease temporally associated with the use of a medicinal (investigational) product.

Any AE that is reported to either the investigators or their designated research associates by a study subject or by medical staff caring for the subject and which meets the criteria will be documented in the participant's chart. The reporting period for participant AEs begins at enrollment (Visit 2) and continues until the subject either completes or withdraws from the study.

All AEs and laboratory abnormalities will be graded according to the Division of AIDS Table for Grading the Severity of Adult and Pediatric Adverse Events (DAIDS AE Grading Table), Version

2.1, July 2017, which can be found on the DAIDS RCC Web site: http://rcc.tech-res.com/tox_tables.htm.

Each AE will be assessed for relatedness to study product. Study investigators will determine AEs to be either definitely related, probably related, possibly related or not related to study product. If the adverse event is, in the investigator's opinion, possibly, probably, or not related to study drug or procedures, then an alternate etiology will be provided by the investigator.

Related AEs \geq Grade 3 will be included in the summary reports provided to the Medical Monitor of the study. Exceptions to expedited reporting are detailed below.

This study uses FDA approved drugs with known common side effects (please refer to the risk section of the protocol for common side effects). The following side effects will not be reported as an EAE unless it increases in severity or becomes prolonged.

Nausea: Report if severity is a Grade 3 or higher

Vomiting: Report if severity is a grade 3 or higher

Diarrhea: Report if severity is a Grade 3 or higher

Rash: Report if severity is a Grade 3 or higher

Serious Adverse Events

A SAE is an adverse drug experience that results in any of the following outcomes:

2. Death.
3. Life-threatening situation - The subject was at risk of death at the time of the adverse event/experience. It does not refer to the hypothetical risk of death if the AE were more severe or were to progress.
4. Inpatient hospitalization or prolongation of existing hospitalization.
5. Persistent or significant disability/incapacity - Any AE having an outcome that is associated with a substantial disruption of the ability to carry out normal life functions, including the ability to work. This is not intended to include transient interruption of daily activities.
6. Congenital anomaly/birth defects - Any structural abnormality in subject's offspring that occurs after intrauterine exposure to treatment.
7. Important medical events/experiences that may not result in death, be life threatening, or require hospitalization may be considered a serious adverse event/experience when, based upon appropriate medical judgment, they may jeopardize the subject and may require medical or surgical intervention to prevent one of the outcomes listed above, i.e., death, a life-threatening adverse event/experience, inpatient hospitalization or prolongation of existing hospitalization, a persistent or significant disability/incapacity, or a congenital anomaly/birth defect. Examples of such medical events/experiences include allergic bronchospasm requiring intensive treatment in an emergency room or at home, blood dyscrasias or convulsions that do not result in inpatient hospitalization, or the development of drug dependency or drug abuse.

In this protocol, spontaneous and elective abortions will be also be considered SAEs.

The reporting period for participant SAEs begins at enrollment (Visit 2) and continues until the subject either completes or withdraws from the study. All SAEs will be reported to the Medical Monitor within 24 hours of site awareness and reported to the IRB per its policies.

It should however be noted that a severe adverse event /experience is not necessarily serious, as the term severe is a measure of intensity while a serious adverse event (SAE) is determined based on the aforementioned regulatory criteria.

Data Safety Monitoring

AEs ≥ Grade 3 or 4 and targeted AEs will be reviewed in real time by study investigators.

Medical Monitor

A medical monitor will be assigned to this study for the purpose of safety oversight. The medical monitor will be notified of all SAEs within 24 hours of site awareness and receive quarterly summary reports of all AEs meeting the previously described criteria.

20. Provisions to Protect the Privacy Interests of Participants

All measures will be taken to ensure information provided by participants is kept confidential. Identifying paper information will be kept in a separate locked office and only accessible by study staff members. Electronic data will be stored on the Redcap server or Emory School of Medicine HIPAA compliant servers, which will be accessible to the study staff only. All study specimens will be labeled with a unique identifier prior to transport to CDC. Identifying information will not be shared with laboratory collaborators at the CDC and they will be unable to link the study ID to any identifying information. Any demographic data shared with CDC will also be stripped of HIPAA identifiers prior to sharing.

21. Economic Burden to Participants

There is no cost to subjects to participate in this study.

22. Consent Process

The consent process will be conducted in a private exam room at the Hope Clinic or electronically via an online e-consent platform (DocuSign) by trained and delegated study staff. The IRB-approved consent form will describe the purpose of the study, procedures, and the risks and benefits of participation. Study staff will review each section of the informed consent with potential participants either in person or remotely (via phone or Zoom). Subjects will be given time to read the consent, ask questions and consider the risks and/or benefits to participation in this research study prior to obtaining their signature. Potential participants may 'pause' the consenting process to review the consent form on their own time to think about participating, discuss with family and friends, etc. Participants will be given direct contact information for the study staff in order to answer any questions or concerns they may have. Once signed, all participants will be provided either a paper or electronic copy of the signed informed consent form (ICF).

Non-English-Speaking Participants: Non-English-speaking subjects will not be enrolled in this study because the study team does not have the resources to enroll and routinely accommodate non-English speaking participants.

Participants who are not yet adults (infants, children, teenagers) Participants who are under the age of 18 will not be enrolled in this study.

Cognitively Impaired Adults Cognitively impaired adults in this study will not be enrolled.

Adults Unable to Consent: Adults who are unable to provide consent for themselves will not be enrolled in this study.

23. Setting

All participant visit will be conducted in a clinic setting at the Hope Clinic.

24. Resources Available

The Hope Clinic routinely meets enrollment goals and has existing partnerships that serve as resources for new potential participants. The study team does not anticipate any issues with recruiting the 40 participants for this study.

The Hope Clinic of Emory University is a free-standing medical research building located in Decatur, GA, and is easily accessible by vehicle or public transportation. There are 8 examination rooms on the top floor in which to see participants. The bottom floor houses the sample processing and storage laboratory. At all times there is a clinician in the clinic available to study staff (all clinicians are on all studies). Should a medical emergency arise, the clinician will manage the immediate situation. The Hope Clinic is located across the street from Emory Decatur Hospital. If needed, Hope Clinic staff would call 911 and have the participant transported there for care.

All study staff have completed all Emory University institutional required research trainings. Prior to working on the study, each staff member is trained thoroughly on each protocol and its supporting documents. There is a dedicated regulatory coordinator who ensures all training and delegation is completed appropriately for each study.

25. Multi-Site Research when Emory is the Lead Site

Not applicable.

26. References

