| Study Population | The population to be studied in this protocol are healthy HIV negative men who have sex with men (MSM) and HIV negative women (to include cisgender and trans females) at risk of HIV infection, who currently do not desire daily PrEP and are willing to undergo study procedures. |
| Sample Size | 20 participants (10 women & 10 MSM). |
| Study Duration for individual participants | The duration of this study is 2 years. Participants will be considered 'on study' for no more than 8 weeks. |
| Study Specific Abbreviations/ Definitions | MSM—Men who have sex with men STI—sexually transmitted infection PrEP—Pre- exposure prophylaxis TAF—tenofovir alafenamide FTC—emtricitabine TDF—tenofovir disoproxil fumarate HIV—Human Immunodeficiency Virus PEP—post-exposure prophylaxis CRAI—condomless receptive anal intercourse DOX—doxycycline BIC—bictegravir CDC—Centers for Disease Control and Prevention WHO—World Health Organization ARV—antiretroviral ED-PrEP—event-driven pre-exposure prophylaxis |
| Funding Source (if any) | Centers for Disease Control and Prevention |

2. Objectives

The purpose of this study is to determine the ability of doxycycline (200mg) and Biktarvy® (200mg) to penetrate mucosal tissues following a single oral dose and retain protective drug levels for extended periods of time.

Public Health Relevance: Event-driven PrEP (ED-PrEP) has been shown to be an effective solution for those who struggle to take a daily regimen of PrEP to prevent HIV; however, biomedical interventions for STI prevention have shown to be effective but have yet to be approved for use. There is limited data on the ability of DOX combined with ARVs to penetrate the mucosal tissues and provide protection against infection. Data regarding mucosal drug exposure will help inform development of multi-purpose event-driven dosing strategies.

Goal: The goal of this study is to understand the distribution of drug within mucosal tissues following a single oral dose of doxycycline and Biktarvy®.

3. Background

Sexually transmitted infections have been proven to increase the risk of HIV infection in men and women. Both men who have sex with men (MSM) and women continue to be disproportionately

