Visit 6 (24 hours post-dose): Approximately 18 mL of blood will be drawn. If the participant has a penis, one urethral swab and one glans swab will be collected. If the participant has a vagina, a vaginal swab will be collected. A urine sample will then be collected from all participants.

Participants who have a vagina will undergo a vaginal/cervical biopsy. All other participants will undergo a rectal biopsy. Participants who complete the vaginal biopsy will have the **option** to also undergo the rectal biopsy at Visit 6. Once the scope (rectal) or the speculum (vaginal) is inserted, additional swabs will be inserted in the rectum or vagina to collect secretions. Then, up to 12 rectal biopsies, or 1 to 2 vaginal and 1 to 2 cervical biopsies will be collected. All participants will be informed not to place anything into the rectum or vagina and abstain from intercourse for 7 days after their biopsy procedure(s) to allow the mucosa to heal.

Vaginal and cervical tissue samples will not be collected in women who are menstruating, pregnant, or have possible cervical or vaginal infection. A pregnancy test will be administered to women of childbearing potential to ensure they are not pregnant. Visit 2 will also be scheduled 7 to 10 days after their last menstrual cycle.

Visit 7 (48 hours post-dose): Approximately 18 mL of blood will be drawn. Then participants will provide a urine sample and self- collect rectal or vaginal fluid swab samples.

Visit 8 (72 hours post-dose): Approximately 18 mL of blood will be drawn. Then participants will provide a urine sample and self- collect rectal or vaginal fluid swab samples.

Visit 9 (96 hours post-dose): Approximately 18 mL of blood will be drawn. Then participants will provide a urine sample and self- collect rectal or vaginal fluid swab samples.

Visit 10 (7 days post-dose): Approximately 18 mL of blood will be drawn. Then participants will provide a urine sample and self- collect rectal or vaginal fluid swab samples.

Timing of procedures after dose: The procedures conducted after dose, particularly those less than 24 hours after dose, should occur as close to the scheduled time points as possible. Protocol deviations will be not filed for visits that occur outside of the target windows but will be noted in source documents.

Contingency visit: If needed, participants may be brought in for additional study visits. This would occur if, for example, screening laboratory results are lost or are inconclusive.

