unknown. In two large studies^{10, 11} including a combined 144,832 clinically indicated procedures, the incidence of serious complications ranged from 0.06 to 0.8% utilizing flexible sigmoidoscopy. Obtaining biopsies may be associated with an increased risk of complications. The best available data on the risk of multiple biopsies comes from studies of dysplasia surveillance among patients with long-standing inflammatory bowel disease, in whom large numbers of “blind” biopsies are obtained throughout the colon for early detection of malignant transformation. In two such studies^{12,13} including a combined 3,011 procedures and a median of eight¹⁴ and 17 biopsies¹³, respectively, there was only one serious complication, for an incidence of approximately 0.33%. More relevant to the present protocol, in a study of subjects undergoing endoscopic procedures exclusively for research purposes⁷⁶, including 64 flexible sigmoidoscopies with a mean of 25 biopsies obtained from the rectosigmoid, there were no major complications. Thirteen subjects experienced minor symptoms (self-limited bleeding and pain), which were not related to the number of biopsies. Thus, the risk of serious complications from the proposed study procedures, even with up to 12 biopsy specimens, is expected to be very low. Of note, [name] has performed >400 such procedures for other research protocols at the Hope Clinic with zero complications.

There is theoretical risk of increased acquisition of HIV or other infection if an HIV negative study participant is exposed soon after the rectal biopsy procedure (i.e. while the mucosal surface is damaged). Similarly, transmission risk from an HIV positive participant to sexual partners may also be heightened with mucosal bleeding. Therefore, study subjects will be counseled not to engage in anal intercourse for 1 week after the procedure.

Biologic samples will be coded with a unique identifier prior to processing and storage for immunologic assays. Therefore, lab personnel will be unable to link specimens with participants. Only designated study personnel will be able to access information to identify specimens of individual participants.

Any abnormalities discovered during the procedure and/or from the safety labs conducted will be discussed with the participant, and a referral will be made to a primary care physician, gastroenterologist or other specialist as needed.

Vaginal and Cervical Biopsies

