| Medical History | X | | | | | | | | | | | |
| Eligibility | | X | | | | | | | | | | |
| Dose Administration | | | X | | | | | | | | | |
| Pregnancy Test | X | | | | | | | | X | | | |
| Urine Sample | X | | | X | X | X | X | X | X | X | X | X |
| Self-Collected Rectal/Vaginal Swabs | | X | | X | X | X | X | | X | X | X | X |
| Staff-Collected Urethral/Glans/Vaginal Swabs | | | | | | | | X | | | | |
| Rectal/Vaginal Biopsy | | | | | | | | X | | | | |
| Blood Volume | 17.2 mL | 2 mL | 18 mL | 18 mL | 18 mL | 18 mL | 18 mL | 18 mL | 18 mL | 18 mL | 18 mL | 18 mL |

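### In any compartment biopsied at 24 h, all later mucosal swabs are post-biopsy, so retention in secretions cannot be separated from a biopsy effect

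*Combined protocol and SAP*

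**What the plan says.** Section 2 (Objectives) gives as part of the purpose whether the drugs penetrate mucosal tissue and "retain protective drug levels for extended periods of time". The end of Section 3 repeats this aim for both men and women.

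Section 6 and Table 1 schedule post-dose mucosal swabs at 1, 2, 4, 8, 24, 48, 72 and 96 h and 7 days. Tissue is taken only at Visit 6 (24 h), by anatomy: "Participants who have a vagina will undergo a vaginal/cervical biopsy. All other participants will undergo a rectal biopsy". Women who have the vaginal biopsy may also choose a rectal one. Swabs precede tissue at that visit: "Once the scope (rectal) or the speculum (vaginal) is inserted, additional swabs will be inserted in the rectum or vagina to collect secretions". The next sentence is "Then, up to 12 rectal biopsies, or 1 to 2 vaginal and 1 to 2 cervical biopsies will be collected".

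Participants are then told to keep the rectum and vagina free of anything inserted and to "abstain from intercourse for 7 days after their biopsy procedure(s) to allow the mucosa to heal". Section 15 speaks of a theoretical infection risk soon after rectal biopsy, "while the mucosal surface is damaged", and lists bleeding among the biopsy risks for both routes. At each of Visits 7 to 10 the instruction is: "Then participants will provide a urine sample and self- collect rectal or vaginal fluid swab samples".

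The Statistical Analysis Plan in Section 18 compares plasma, swab and tissue concentrations at 24 h only. No passage asks for blood on a swab to be recorded, or says how swab values after 24 h will be reported.

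**The concern.** Within a biopsied compartment the condition of the mucosa changes once, at 24 h, and does so for every participant at the same time. There is no randomised biopsy time and no planned unbiopsied group. Time since dose beyond 24 h and biopsy status therefore coincide completely in that compartment.

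Blood or wound fluid on a late swab would mix drug from the circulation into a sample meant to show the level in secretions. If secretions hold less drug than plasma, the measured level is too high and looks like retention. If they hold more, it is too low.

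Any comparison of persistence between the rectal and vaginal routes has the same weakness, because biopsy number and specimen size differ by route. What is at stake is what the trial can say about retention, since the late swabs are its only mucosal samples after 24 h.

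**Working it through.** The plan states no figure to reproduce on this point. The check has four steps.

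**1. Swab times against the biopsy (Section 6, Table 1).**
- Pre-biopsy: 1, 2, 4, 8 and 24 h, which is 5 of 9. The 24 h swab counts here because tissue is taken after it.
- Post-biopsy: 48, 72, 96 and 168 h, which is 4 of 9. Subtracting 24 h gives 24, 48, 72 and 144 h, or 1, 2, 3 and 6 days after biopsy. All lie inside the 7-day period.
- Share of follow-up after the biopsy: (168 − 24)/168 = 0.857.

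**2. What blood on a swab could do to one value.** The documents give neither the ratio R of secretion to plasma concentration nor the fraction f of the sample that is blood, so both are assumed. Blood is treated as having the plasma concentration, which is a simplification. Measured/true = (1 − f) + f/R.

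| R | f = 5% | f = 20% | f = 50% |
|---|---|---|---|
| 0.1 | 1.45 | 2.80 | 5.50 |
| 0.3 | 1.12 | 1.47 | 2.17 |
| 1 | 1.00 | 1.00 | 1.00 |
| 10 | 0.955 | 0.82 | 0.55 |

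The bias can go either way and can be nil.

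**3. What it could do to an apparent half-life.** No half-life is planned or stated, so this is illustration only. Fit a log-linear line to 24, 48, 72, 96 and 168 h (mean 81.6 h, sum of squared deviations 12,211.2) and multiply all four post-biopsy values by a constant g. The slope shifts by 57.6/12,211.2 = 0.0047 × ln(g) per hour. The apparent half-life is ln 2 / (ln 2/true half-life − 0.0047 × ln g).

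| Assumed true half-life | g = 0.5 | g = 2 | g = 4 |
|---|---|---|---|
| 12 h | 11.4 h | 12.7 h | 13.5 h |
| 18 h | 16.6 h | 19.7 h | 21.7 h |
| 24 h | 21.6 h | 27.1 h | 31.0 h |

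The result depends heavily on the points used. With a true 18 h and g = 2.8, a clean 24 h value and a contaminated 96 h value alone give 72 × ln 2 / (72 × ln 2/18 − ln 2.8) = 28.6 h. The five-point fit with the same g gives about 20.6 h. A simple ratio of a late value to the 24 h value carries the whole factor g.

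**4. Biopsy load by route.** Section 6 gives up to 12 rectal specimens about 1.0 mm thick, against 1 to 2 vaginal (about 2.4 mm thick) plus 1 to 2 cervical. Cervical thickness is not stated and is assumed equal to vaginal.
- Count: 12 against 2 to 4, so 12/4 = 3 to 12/2 = 6 times as many rectal biopsies at the maximum.
- Summed thickness: 12 × 1.0 = 12.0 mm against 2 × 2.4 = 4.8 to 4 × 2.4 = 9.6 mm.
- Thickness squared, as a rough proxy for area: 12 × 1.0² = 12 against 2 × 2.4² = 11.5 to 4 × 2.4² = 23.0.

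The routes differ, but which carries the larger wound depends on the measure.

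**The case against.** The strongest reply is that no planned analysis is touched. Both endpoints in Section 4 and every SAP test use 24 h data, the 24 h swabs precede the biopsies, and no slope or half-life is proposed. This stands in full.

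A second reply is that the stated aim concerns retention in tissue, not in secretions. That is the literal wording. But tissue is sampled at one time only, so it cannot show retention, and the swab series is the only mucosal data that can bear on it.

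A third is that the healing instruction is precautionary and does not show that bleeding lasts to day 6. Section 15 cites a research series averaging 25 biopsies in which 13 subjects had only minor symptoms, unrelated to biopsy number. Staff also ask about symptoms after the biopsy. This makes a large effect less likely, but a symptom enquiry does not show whether a given swab carried blood.

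Three stronger readings might tempt a reader, and the documents do not support them:
- *Every late swab comes from biopsied mucosa.* Section 6 withholds vaginal and cervical biopsy in menstruation or possible infection, and rectal biopsy is optional for women who have the vaginal one. Some late swabs may come from unbiopsied mucosa. Whether women give rectal swabs at all is unclear, since the synopsis lists both kinds of secretion and Section 6 lists one or the other.
- *Men carry the heavier wound load.* The contrast is by anatomy and route, women may have both biopsies, and step 4 leaves the direction open.
- *Late swabs sample the biopsy wound itself.* Rectal biopsies are taken 10 cm above the anal opening and the depth of the self-collected swab is not stated. The compartment is the same; the site may not be.

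**Conclusion.** The point holds as a limit on descriptive retention data. In a biopsied compartment, 4 of 9 swab times and 144 of 168 h of follow-up are post-biopsy, with no overlap in time that would let a biopsy effect be separated from drug kinetics. This part rests on the schedule alone and needs no assumption.

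The size and direction of any bias are not known. The factors in step 2 (0.55 to 5.5) and the half-lives in step 3 rest wholly on assumed values. A reader might take the 28.6 h figure as the expected distortion; it comes from two points and an assumed 20% blood fraction three days after biopsy.

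A reader might also infer that the rectal against vaginal comparison at 24 h is compromised. It is not: the primary and secondary endpoints and all SAP tests are unaffected. The change is worth making because visible blood cannot be reconstructed if it is not recorded at collection.

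Two related points sit at the same visit. The row "Staff-Collected Urethral/Glans/Vaginal Swabs" in Table 1 applies only at 24 h while the other swabs are self-collected, so a comparison of 24 h with later values also crosses a change of collection method. The self-collected swabs at Visits 7 to 10 also fall within the 7 days in which nothing is to be inserted.

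**What to change.** 1. Add a CRF field at Visits 7 to 10 for visible blood on each rectal or vaginal swab, and record the site and number of biopsies taken at Visit 6.
2. State in the SAP that swab concentrations from 48 h to 7 days are descriptive, labelled post-biopsy where the compartment was biopsied, and reported separately from the 1 to 24 h values. Add a sensitivity analysis that excludes blood-stained swabs.
3. Show swabs from unbiopsied compartments separately as a reference where they exist. They may be few and cannot carry the conclusion. Plasma is a different compartment and cannot replace them.
4. Limit any statement on retention, or on route differences in persistence, from biopsied compartments accordingly.
5. Reconcile the passages in Section 6 on self-collected swabs at Visits 7 to 10 and on inserting nothing for 7 days after biopsy.

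The cost is a few CRF entries and a few SAP sentences, with no added visit, sample or procedure. The downside is fewer usable late swabs in the sensitivity analysis and a more limited retention claim.
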